EmStop, Inc.

CAPTURE-1: Controlled Arterial Protection to Ultimately Remove Embolic Material

Clinical Study Protocol

Protocol Number: EMS-CL-5000

Revision: B (10Oct2023)

ClinicalTrials.gov NCT Number: NCT06103591

EmStop, Inc. [name] [contact]

THIS STUDY PROTOCOL CONTAINS CONFIDENTIAL INFORMATION FOR USE BY THE INVESTIGATORS AND THEIR DESIGNATED REPRESENTATIVES PARTICIPATING IN THE STUDY. IT SHOULD BE HELD CONFIDENTIAL AND MAINTAINED IN A SECURE LOCATION. IT SHOULD NOT BE COPIED OR MADE AVAILABLE FOR REVIEW BY ANY UNAUTHORIZED PERSON OR FIRM.

Contents of this document are confidential information belonging to EmStop, Inc. and BRIGHT Research Partners. Contents may not be used for any purpose whatsoever without specific written consent from EmStop, Inc. and BRIGHT Research Partners.

Sponsor Signatures

Signature:	[name] approve this document [name] approve this document 10/5/2023 5:16:58 PM PDT 9A52421D23B14FBA82CEEBF245D12E34	Date:	10/5/2023
	Sponsor [name], Chief Executive Officer, EmStop, Inc.		
Signature:	DocuSigned by [name] [name] I approve this document 10/10/2023 11:57:13 AM PDT 90B4839166F245FAA6A7D470A7F0CE1B	Date:	10/10/2023
	Study Director (CRO) [name], Assoc. Study Director, BRIGHT Research	Partners	
Signature:	[name] [name] approve this document 10/10/2023 11:53:46 AM PDT B9331EF4F03B4104A7B59288D638B192	Date:	10/10/2023
	Statistician (CRO)		

[name], Chief Scientific Strategist, BRIGHT Research Partners

EmStop, Inc.		CLINICAL STUDY PROTOCOL SYNOPSIS EmStop Study Number: EMS-CL-5000	
Study Title	CAPTURE-1: Material	Controlled Arterial Protection to Ultimately Remove Embolic	
Identifying Regulatory Numbers	FDA IDE num	ber – G220288	
Study Objective	The objective of this study is to demonstrate safety and investigate performance of the EmStop Embolic Protection System when used as indicated.		
Device Description	The EmStop Embolic Protection System (EmStop System) is a catheter-based filter system that captures and removes debris dislodged during transcatheter aortic valve replacement (TAVR) procedures. The EmStop System is composed of a preloaded introducer sheath, delivery catheter, and filter sheath.		
Proposed Device Indications for Use	The EmStop Embolic Protection System is indicated for use as an embolic protection device to capture and remove thrombus/debris while performing transcatheter aortic valve replacement procedures. The diameters of the aorta at the site of filter placement should be between 25 – 40 mm.		
Study Design	The investigation is a prospective, multi-center, single arm feasibility study. Subjects will undergo treatment with a currently marketed TAVR device and the EmStop Embolic Protection System and will then be followed to 30 days post- procedure. This is a treatment-only feasibility investigation intended to capture and characterize outcomes, especially safety outcomes, with the EmStop System.		
Number of Sites & Subjects	The study will be conducted in up to 2 investigational sites in the U.S. This study will enroll up to 15 subjects.		
Study Population	The population for this study is subjects with severe native aortic valve stenosis who meet clinically approved indications for TAVR. The investigation population aligns with the EmStop System proposed indications. The study will be conducted in adult subjects and does not include any other age, gender, or racial and ethnic origin restrictions.		
Primary Safety and Performance Endpoints	The primary sa days, defined a Al Al Ad th The primary po defined as suc EmStop Syste	afety endpoint for the study is the occurrence of MACCE at 30 as a composite of the following VARC-2 defined components: I-cause mortality I stroke (disabling and non-disabling) cute kidney injury (AKI) Stage 2 or 3 (including renal replacement erapy) within 72 hours erformance endpoint for the study is device procedural success, ccessful insertion, deployment, positioning, and removal of the m in the absence of device interference.	

EmStop, Inc.		CLINICAL STUDY PROTOCOL SYNOPSIS EmStop Study Number: EMS-CL-5000
Secondary Endpoints	The following s Gross partic indep Avera by an Total (DWI) (asse and ta volum	secondary endpoints will be evaluated: secondary endpoints will be evaluated: s and histologic evaluation of captured embolic debris, including le presence, count, size, and composition (assessed by an endent pathology core laboratory) age number of captured particles ≥140 µm in diameter (assessed independent pathology core laboratory) acute infarct burden, as measured by diffusion-weighted imaging) within 14 days pre-procedure and at 18-36 hours post-procedure ssed by an independent reader). This outcome will be evaluated abulated to include total lesion count, average (mean) lesion the and median lesion volume.
	Occur	rrence of Transient Ischemic Attack (TIA)
Study Eligibility Criteria	Patients must Clinical inclusion 1. Betwe	meet all the following inclusion criteria: on criteria en 21 and 90 years of age at the time of consent
	2. Meets replac comm	FDA approved indications for transcatheter aortic valve ement (TAVR) procedure on a native aortic valve using a ercially available Abbott or Medtronic transcatheter heart valve
	3. Willing author	and able to provide written informed consent and written HIPAA ization prior to initiation of study procedures
	4. Willing assess	and able to comply with the protocol-specified procedures and sments
	Angiographic I	nclusion Criteria (assessed via computed tomography)
	5. Subjec positio	ct anatomy is compatible with correct device deployment and oning with:
	 Ability sheath 	to achieve access with a 21 French equivalent femoral access າ
	 Ascen 	ding aorta length ≥8 cm
	Ascen	ding aorta/aortic arch diameter is > 25 or ≤40 mm
	Ascen diseas	ding aorta or aortic arch exhibits ≤ Grade 1 atheromatous e and limited wall calcification
	Patients must	not meet any of the following exclusion criteria:
	1. Requir	res urgent or emergent TAVR procedure
	2. Contra	aindicated to MRI

EmStop, Inc.		CLINICAL STUDY PROTOCOL SYNOPSIS EmStop Study Number: EMS-CL-5000
;	3. Previo	ously implanted aortic or mitral valve bioprosthesis
	4. Hepat	ic failure (Child-Pugh class C)
	5. Hyper peripr	coagulable state that cannot be corrected by additional ocedural heparin
	 Plann proce TAVR Diagn obtain intrac 	ed to undergo any other cardiac surgical or interventional dure (e.g., concurrent coronary revascularization) during the procedure or within 30 days prior to the TAVR procedure. NOTE: ostic cardiac catheterization is permitted up until baseline MRI is red. Once baseline MRI is obtained, no additional intra-aortic or ardiac procedure may occur.
	7. Acute proce	myocardial infarction within 30 days of the planned index dure
5	3. Renal mL/m	failure, defined as estimated glomerular filtration rate (eGFR) <30 in
). Docur prior s baseli	nented history of stroke or TIA within the prior 6 months, or any stroke with a permanent major disability or deficit (NIHSS >1 at ne)
	I0. Left v proce	entricular ejection fraction ≤30% within 3 months prior to dure
	I1. Histor study sensit pre-tro	y of intolerance, allergic reaction, or contraindication to any of the medications, including heparin, aspirin, clopidogrel, or a ivity to contrast media or anesthesia that cannot be adequately eated
	12. Know	n allergy or sensitivity to nickel-titanium
	I3. Active (>38°	e endocarditis or ongoing systemic infection, defined as fever C) and/or white blood cell (WBC) >15,000 IU
	14. Undei	going therapeutic thrombolysis
	15. Histor	y of bleeding diathesis or a coagulopathy
	I6. Know child-l test w	n or suspected to be pregnant, or is lactating; female subjects of bearing potential must have a negative serum or urine pregnancy ithin 48 hours prior to the index study procedure.
	I7. Curre	ntly participating in another drug or device clinical study

EmStop, Inc.		CLINICAL STUDY PROTOCOL SYNOPSIS EmStop Study Number: EMS-CL-5000	
	 18. Any other clinical reason, as deemed by the investigators of the study, by which the patient would not be an appropriate candidate for the study 19. Vulnerable subject populations (e.g., incarcerated or cognitively challenged adults) 		
Study Duration	Enrollment is expected to take approximately 3 months. Each study subject will actively participate in the study through 30-day follow-up. The overall study duration, from screening the first patient to the final follow-up visit, data analysis, and final report, is expected to be approximately 6-9 months.		
Study Sponsor	EmStop, Inc. Detailed contact information is maintained in a separate Sponsor Contact List managed by the CRO		

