During the TAVR procedure, cerebral emboli have been shown to originate from atheromatous plaques within the aorta and from the degenerate stenotic aortic valve itself. An analysis on 3,687 subjects from the CoreValve (Medtronic) U.S. Extreme Risk and High Risk Pivotal Trials and Continued Access Registry reported a stroke rate of 4.1% in the first 10 days post-TAVR (Kleiman). The PARTNER trial, which evaluated the Sapien device (Edwards Lifesciences) in 2,621 subjects, reported cerebrovascular events in 3.8% at 30 days (Kapadia). This data illustrates the clinical need for embolic protection, which may have a significant role to play in the continued safety and adoption of TAVR as a treatment, especially for the intermediate risk patient population for which TAVR is currently being offered.

Several embolic protection devices are in different stages of investigation in the U.S. PROTECTED TAVR is a landmark randomized control clinical trial currently underway comparing non-embolic protected TAVR to embolic protected TAVR using the Sentinel device (Boston Scientific, Inc.), which is the only embolic protection device currently cleared by FDA.

The embolic protection products that are currently approved or under investigation are standalone from the TAVR systems that require separate procedures with separate anatomical access points, thus increasing the complexity and risk. The investigational device is intended to provide a transformative development in the safety and ease of use of embolic protection products by providing full cerebral protection using a technology platform that is integrated into the normal workflow of the TAVR procedure.

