3.1.2 Delivery catheter

A single lumen, braid-reinforced catheter that facilitates delivery of the filter sheath into the aortic arch and controls deployment of the filter via internal actuation wires and a thumb slider

interface on the proximal handle (**Figure 3**). The distal end of the delivery catheter handle contains release clips for connection with the filter sheath. The delivery catheter has a radiopaque distal tip and a nonradiopaque (yellow) marking on the shaft to identify the shaft outside diameter (OD) transition; the force required to remove the device changes at this transition. A Luer connector on the proximal end of the handle is used for flushing.

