3.2 Principle of Operation / Mechanism of Action

The EmStop System provides embolic protection during TAVR procedures while preserving virtually the same sequence and number of steps as unprotected TAVR. The EmStop System contains a central lumen for TAVR device insertion, which eliminates the need for a concomitant vascular entrance point.

After femoral access is obtained and the guidewire is advanced to the targeted location, the EmStop System is loaded onto the guidewire and advanced to the targeted location. Next, the filter sheath is advanced under fluoro guidance, and the filter is deployed in the target location within the ascending aorta (i.e., between the innominate takeoff and the aortic valve; the specific location may vary from patient to patient). The TAVR device is inserted through the EmStop System, and the procedure is conducted per the TAVR device IFU. After the TAVR procedure, the EmStop device is withdrawn, and the emboli captured in the filter is removed from the patient.

The EmStop expanded filter provides filtration, collection, and removal of emboli liberated into the proximal aorta during the TAVR procedure. The filter is deployed in the ascending aorta proximal to any branch artery, thus protecting the brain and vital organs from embolic damage. Embolic material may be aspirated through the filter sheath during the TAVR procedure. Upon completion of the TAVR procedure, the filter and the captured embolic material are withdrawn into the sheath and removed from the patient.

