6.5 Subject Eligibility Criteria

6.5.1 General Inclusion Criteria

Subjects must meet all the following inclusion criteria:

Clinical inclusion criteria

- 1. Between 21 and 90 years of age at the time of consent
- 2. Meets FDA approved indications for transcatheter aortic valve replacement (TAVR) procedure on a native aortic valve using a commercially available Abbott or Medtronic transcatheter heart valve

- 3. Willing and able to provide written informed consent and written HIPAA authorization prior to initiation of study procedures
- 4. Willing and able to comply with the protocol-specified procedures and assessments

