6.5.2 Angiographic Inclusion Criteria (assessed via computed tomography)

- 5. Subject anatomy is compatible with correct device deployment and positioning with:
 - Ability to achieve access with a 21 French equivalent femoral access sheath
 - Ascending aorta length ≥8 cm
 - Ascending aorta/aortic arch diameter is ≥ 25 or ≤40 mm
 - Ascending aorta or aortic arch exhibits ≤ Grade 1 atheromatous disease and limited wall calcification

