7.1 Screening Visit

The study team will screen patients for the study. Screening is defined as the process of reviewing a patient's medical records against the study eligibility criteria to determine if the patient is eligible to enroll in the study. It is expected that the medical records will contain adequate information to determine if a patient meets most of these criteria; this includes the computed tomography (CT) completed as part of the standard of care TAVR screening process. The investigator will visually assess the CT imaging to ensure angiographic inclusion criteria are met.

If the investigator (or designee) determines the patient meets all clinical inclusion and exclusion criteria (except criteria verified by blood or urine testing after consent), they can be consented for study participation, after which all remaining non-angiographic eligibility criteria will be verified prior to the procedure.

Sites will be required to maintain a screen failure log that contains rationale for subjects who became screen failures after consent.

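### The atheroma and calcification inclusion bullet joins the ascending aorta and the arch with *or*, so read literally one compliant segment is enough, even when the filter site is diseased

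*Combined protocol and SAP*

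**What the plan says.** Section 6.5.2 lists, as one of four bullets under inclusion criterion 5: "Ascending aorta or aortic arch exhibits ≤ Grade 1 atheromatous disease and limited wall calcification". The synopsis carries the same bullet, with the same joining word: "aorta or aortic arch exhibits ≤ Grade 1 atheromatous".

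The lead-in to criterion 5 is "Subject anatomy is compatible with correct device deployment and positioning with", followed by the bullets. Section 6.5.1 sets the rule for combining criteria: "Subjects must meet all the following inclusion criteria".

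On the device, section 3.1.2 says that the delivery catheter "facilitates delivery of the filter sheath into the aortic arch", and section 3.2 says that "the filter is deployed in the target location within the ascending aorta". Section 2.0 states that during TAVR "cerebral emboli have been shown to originate from atheromatous plaques within the aorta".

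On who applies the limit, section 7.1 says: "The investigator will visually assess the CT imaging to ensure angiographic inclusion criteria are met". The independent readers described in section 9.0 cover the captured debris and the MRIs, not the screening CT.

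**The concern.** An inclusion condition of the form *A or B complies* is met by either one. Taken at its word, the bullet lets compliance in one segment stand in for disease in the other. The more awkward case is a subject whose ascending aorta is above Grade 1 or heavily calcified but whose arch is clean: the bullet is met, although the filter is to be opened in the diseased segment. The reverse case, a clean ascending aorta and a diseased arch, also passes, although the system travels through the arch.

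Aortic disease bears on what the study measures. Stroke is a component of the primary safety endpoint, DWI infarct burden is a secondary endpoint, and positioning of the device is part of the primary performance endpoint. The protocol itself names aortic plaque as an embolic source, so admitting such subjects may add embolic risk. It would also mix different anatomies in results meant to inform a pivotal study.

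**Working it through.** No formula in the plan depends on this bullet, and there is no stated figure to reproduce. The check is a comparison of texts and a truth table.

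**1. Is the wording consistent, and is it limited elsewhere?** The synopsis and 6.5.2 agree, so this is not a slip in one copy. None of the 19 exclusion criteria in 6.5.3 mentions aortic atheroma or calcification. No section says that both segments must comply, that the worse one governs, or that only the filter site counts.

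**2. What does each reading admit?** Call a segment compliant if it is within the Grade 1 limit and has limited wall calcification. Take the filter site as the ascending aorta, per 3.2.

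| Ascending aorta compliant | Arch compliant | Literal *or* | Each segment must comply | Filter site only |
|---|---|---|---|---|
| yes | yes | met | met | met |
| yes | no | met | not met | met |
| no | yes | met | not met | not met |
| no | no | not met | not met | not met |
| **Combinations admitted** | | **3 of 4** | **1 of 4** | **2 of 4** |

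The third row is decisive. A literal *or* admits it, and neither of the two readings that the device description could support does. The second row is where those two readings differ, so it needs a decision from the sponsor. These are logical combinations, not proportions of patients.

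**3. How does this fit the device description?** For the third row, the filter would be deployed in a segment that fails the limit, which is hard to square with the criterion 5 lead-in. For the second row, the system passes through a segment that fails the limit. Section 3.2 places the filter upstream of the first arch branch. By inference, debris loosened in the arch would arise either before the filter is open or downstream of it.

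**4. Would another step catch it?** Section 7.1 relies on the investigator's visual CT read. After consent it calls for verification of the remaining criteria other than the angiographic ones. The recheck in 7.4 refers to the general inclusion and exclusion criteria. No second read of the aortic anatomy is described.

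**5. How much does one subject weigh?** Section 6.2 allows up to 15 subjects at up to 2 sites, and section 8.1 keeps every enrolled subject in the primary analysis. One subject is 1/15 = 6.7 percentage points of either primary endpoint, and more if fewer are enrolled. If two sites read the bullet differently, anatomy and site are confounded.

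**The case against.** The strongest reply is that meeting the bullet is not the same as meeting the criterion. The lead-in to criterion 5 asks for suitable anatomy overall, the investigator looks at the CT, and exclusion 18 lets the investigator refuse any unsuitable candidate. This stands in part. It makes enrolment of a heavily diseased subject less likely, and a reader who inferred that the plan will enrol such subjects would go beyond the documents. But the lead-in may equally be read as defined by its bullets, and neither it nor exclusion 18 states a rule on aortic disease that two sites would apply alike.

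A second reply is that the phrase may name one region judged as a whole; the diameter bullet just above joins the same two segments with a slash. That is a fair reading, and many investigators may adopt it. It shows that the bullet is ambiguous, which is a reason to settle the wording.

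A third is that the intent is not stated. The proposed indication limits diameter only where the filter is placed, so a limit at the filter site alone is conceivable. This stands: a reader might infer that both segments were always meant, but the documents do not say so. Even then, the literal *or* is wrong for the third row of the table.

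Finally, endpoints are summarised descriptively and the sample size is not power-based, so no test, alpha level or sample-size figure changes. That is correct and limits the weight of the point.

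**Conclusion.** The point holds as a defect in a stated eligibility rule. Read literally, the bullet accepts one compliant segment in place of two, including the case in which the filter site itself fails the limit. That contradicts the lead-in to criterion 5 and does not fit sections 3.1.2 and 3.2. The existing safeguards reduce the consequence without removing it.

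Two stronger readings are not supported. A number of affected subjects cannot be given, because the documents contain no prevalence of disease confined to one segment and do not show how sites read the bullet. Nor do the documents show that the wording raises the stroke rate: section 2.0 names aortic plaque as a source of emboli during TAVR generally and gives no estimate for this device crossing a diseased segment. *May add embolic risk* is as far as they go.

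The conclusion rests on the plain meaning of *or* in an entry condition and on the filter being deployed in the ascending aorta. It should be corrected, but it calls for no statistical redesign.

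**What to change.** In the synopsis and in 6.5.2, replace *or* with wording that names the segment or segments that must each meet the atheroma and calcification limit. Compliance in one segment should not be able to stand in for disease in another segment that the device needs. Reconcile the bullet with the criterion 5 lead-in and with sections 3.1.2 and 3.2. The sponsor should confirm whether the limit covers both segments or the filter site only; that is a clinical decision and is not proposed here.

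The cost is a short protocol amendment with IRB approval before implementation (section 12.9), and possibly a few more screen failures. The same screening CT serves, and no analysis changes.

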1.0 ABBREVIATIONS

The following is a list of abbreviations used in the body of this document. Abbreviations solely used in tables (e.g., table headers) are described in the table footer and are not included below.

ADE	Adverse device effect
AE	Adverse event
AS	Aortic valve stenosis
CFR	Code of federal regulations (U.S.)
CRF	Case report form
(e)CRF	(electronic) case report form
CRO	Contract Research Organization
DWI	Diffusion-weighted imaging
EDC	Electronic data capture database
FDA	Food and Drug Administration (U.S.)
GCP	Good clinical practice
HIPAA	Health Insurance Portability and Accountability Act
ICF	Informed consent form
ICH	International Conference on Harmonization
IFU	Instructions for use
IRB	Institutional review board
IRB ISO	Institutional review board International Organization for Standardization
IRB ISO MoCA	Institutional review board International Organization for Standardization Montreal cognitive assessment
IRB ISO MoCA mRS	Institutional review board International Organization for Standardization Montreal cognitive assessment Modified Rankin Scale
IRB ISO MoCA mRS NIHSS	Institutional review board International Organization for Standardization Montreal cognitive assessment Modified Rankin Scale National Institute of Health Stroke Scale
IRB ISO MoCA mRS NIHSS PI	Institutional review board International Organization for Standardization Montreal cognitive assessment Modified Rankin Scale National Institute of Health Stroke Scale Principal investigator
IRB ISO MoCA mRS NIHSS PI SAE	Institutional review board International Organization for Standardization Montreal cognitive assessment Modified Rankin Scale National Institute of Health Stroke Scale Principal investigator Serious adverse event
IRB ISO MoCA mRS NIHSS PI SAE SAP	Institutional review board International Organization for Standardization Montreal cognitive assessment Modified Rankin Scale National Institute of Health Stroke Scale Principal investigator Serious adverse event Statistical analysis plan
IRB ISO MoCA mRS NIHSS PI SAE SAP SAVR	Institutional review board International Organization for Standardization Montreal cognitive assessment Modified Rankin Scale National Institute of Health Stroke Scale Principal investigator Serious adverse event Statistical analysis plan Surgical aortic valve replacement
IRB ISO MoCA mRS NIHSS PI SAE SAP SAVR TAVR	Institutional review board International Organization for Standardization Montreal cognitive assessment Modified Rankin Scale National Institute of Health Stroke Scale Principal investigator Serious adverse event Statistical analysis plan Surgical aortic valve replacement Transcatheter aortic valve replacement

